Achilles Pain Block

NCT 03316378

Date of Document: 4/29/19

[figure not shown]
Date study protocol initially approved by the IRB: 1/27/2016

Date study was most recently approved by the IRB: 8/13/2018

Study design

In this mechanistic, non-randomized controlled trial, all participants repeated testing twice in the following order within a single laboratory-based testing session: 1) pain-rating with activity, 2) movement analysis during high- and low-level tasks, 3) pain psychology questionnaires; 4) quantitative sensory testing (See figure below). The only difference in procedure between groups was that the AT group received an anesthetic injection after the first set of tests. For participants with bilateral AT the more painful side was designated the involved side for testing and injection. A sports medicine physician used sonographic guidance to inject 4 mL of 0.5% ropivacaine superficial and deep to the tendon to ensure coverage of the painful region. This dose was chosen based on clinical experience of the amount of ropivacaine needed to numb the area for minimally-invasive outpatient procedures. To minimize the risk of infection sterile technique was used, including sterile gloves, area of injection scrubbed, sterile gel, and a sterile transducer cover. The onset for ropivacaine was 10-20 minutes and pain relief lasted for 6-8 hours. Repeat testing began 30 minutes after the injection. Participants with AT were contacted 1-day and 1-week following testing to ask about any injection-related adverse events (e.g. increased pain, infection). All participants were contacted 1-week after testing to complete the pain catastrophizing scale (PCS).

Figure 1. All participants completed two sets of testing. The group with Achilles tendinopathy pain received a local anesthetic injection prior to repeat testing. The control group without Achilles tendinopathy pain did not receive an injection prior to the second set of testing.

Statistical Analysis

A priori power analysis determined that a sample size of 20 per group was needed to detect effect sizes (between groups ≥ 0.91 , between repeat tests ≥ 0.68) less than or equal to published results for ankle power (mean difference = 0.9 W/kg, SD = 0.9 W/kg)¹, kinesiophobia (minimal detectable change = 5.6, SD = 5.7)², and pressure pain threshold (group difference = 171.8 kPa, SD = 174.8 kPa)³ with a power $\geq 80\%$ and statistical significance defined as $P \leq 0.05$ (**Table 1**). Because 3 participants with AT had insufficient pain relief from the

anesthetic injection, an additional 3 participants were recruited per group to ensure adequate power, resulting in a final sample size of 46. Sample characteristics were compared between groups using independent samples t-test for parametric data, Mann-Whitney U test for non-parametric data, or Chi-square test for categorical data. Changes in Achilles tendon pain from pre-injection to post-injection were compared with Wilcoxon Signed Ranks tests. Mixed effects ANOVAs were used to examine the effects of group, time, and a group*time interaction for motor performance, pain psychology, and quantitative sensory testing. The type I error rate for the ANOVAs was maintained at 0.05 by using Bonferroni adjustment for multiple comparisons (3 tests for motor performance, 2 tests for pain psychology, 3 tests for quantitative sensory testing). Post-hoc comparisons were performed to examine significant interaction effects and p-values were adjusted using a Bonferroni adjustment for the number of time points compared (2 for TSK, 3 for PCS, 4 for quantitative sensory test). Pearson correlations examined relationships between the magnitude of change with an anesthetic injection of identified indicators of altered central processing in the AT group.

Primary outcome / dependent variable	Assumed SD	Detectable difference	Published difference
Specific Aim 1.1, n=40, between groups, detectable effect size ≥ 0.91			
PPT (Central sensitization)	174.8 kPa ³	158.9 kPa	171.8 kPa ³
TSK (Psychological factor)	5.7 ²	5.2	MDC= 5.6 ²
Ankle power (Motor control)	0.9 W/kg ¹	0.8 W/kg	0.9 W/kg ¹
Specific Aim 1.2, n=20, repeated measures, detectable effect size ≥ 0.68			
PPT (Central sensitization)	28%	19%	25.8% ⁴
TSK (Psychological factor)	5.7 ²	3.8	MDC= 5.6 ²
Ankle power (Motor control)	0.9 W/kg ¹	0.6 W/kg	0.9 W/kg ¹

References

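### Adverse events are asked about only in tendinopathy participants and only as injection-related, so no enquiry is described for harm from the testing or for any harm in controls

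*Combined protocol and SAP*

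**What the plan says.** All of the relevant text is in the Study design section of the combined protocol and SAP.

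- **Adverse-event enquiry:** "Participants with AT were contacted 1-day and 1-week following testing to ask about any injection-related adverse events (e.g. increased pain, infection").
- **Contact with controls:** "All participants were contacted 1-week after testing to complete the pain catastrophizing scale (PCS"). The scale is the only stated purpose of this contact, and it is the only follow-up contact described for controls.
- **What participants do:** "In this mechanistic, non-randomized controlled trial, all participants repeated testing twice". The test set includes "2) movement analysis during high- and low-level tasks".
- **Timing in the AT group:** "Repeat testing began 30 minutes after the injection", and "The onset for ropivacaine was 10-20 minutes and pain relief lasted for 6-8 hours".
- **Who the controls are:** "The control group without Achilles tendinopathy pain did not receive an injection prior to the second set of testing".

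The Statistical Analysis section describes no adverse-event analysis.

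**The concern.** An AT participant is exposed to two things that could cause harm: the injection, and a second round of movement tasks on a painful tendon that has been anesthetised. The described enquiry is framed around the first. Framing it that way puts a judgement of cause ahead of the recording of the event. The usual order is the reverse: record whatever happened, then assign a presumed cause. An event that the participant or the caller puts down to the tasks falls outside the enquiry as described.

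Controls go through the same two rounds of testing. They are contacted a week later, but no question about harm is described for them.

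What is at stake is how completely harms are ascertained and how a safety statement may be worded. A report of no events would, on this description, cover injection-related events in AT participants only. A reader could easily take it to cover the whole study procedure in everyone.

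**Working it through.** The adverse-event sentence contains no statistical figure, so the main check sets the statements side by side. Arithmetic then shows how much a group of this size can say about harms.

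**1. Group size.** The Statistical Analysis section plans 20 per group, adds 3 per group, and gives a final sample of 46. This agrees: 20 + 3 = 23 per group, and 2 × 23 = 46. The planned 20 also reproduces. For the stated between-group effect size of 0.91 at 80% power, with alpha 0.05 taken as two-sided (sidedness is not stated), an exact two-sample t-test calculation gives 19.96, rounded up to 20, with power 0.801 at 20 per group. The point here does not affect that calculation.

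**2. Are the repeat tasks done under the block?** Stated onset is 10–20 minutes, repeat testing starts at 30 minutes, and stated relief lasts 6–8 hours (360–480 minutes). Since 20 < 30 < 360, repeat testing starts after onset and well before relief is stated to end. The length of the test set is not given, and 3 AT participants are reported to have had insufficient relief. The safe statement is that some of the repeated tasks are done under the block.

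**3. Do the contacts come after the block has worn off?** The first contact is at 1 day, about 24 hours, against a maximum stated relief of 8 hours. Both AT contacts therefore fall when pain could be felt again.

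**4. Coverage of the enquiry as described.**

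| Possible event | AT group | Controls |
|---|---|---|
| Put down to the injection | Asked at 1 day and 1 week | Not applicable (no injection) |
| Increased pain, cause unclear | Probably captured, as increased pain is a named example | No enquiry described |
| Put down to the testing tasks | No enquiry described | No enquiry described |
| Any other event | No enquiry described | No enquiry described |

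**5. Precision with 23 AT participants.** If no events are recorded:

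- one-sided 95% upper bound: 1 − 0.05^(1/23) = 0.122, or 12.2%
- two-sided 95% exact (Clopper-Pearson) upper bound: 1 − 0.025^(1/23) = 0.148, or 14.8%

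The chance of seeing at least one event is 1 − (1 − p)^23. The true rates below are assumptions, as the documents give none:

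| Assumed true rate p | Chance of at least one event in 23 |
|---|---|
| 2% | 37% |
| 5% | 69% |
| 10% | 91% |

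These figures follow from the group size and would be the same whatever question was asked. They do not measure the effect of the narrow wording. They show that even a complete enquiry says little about uncommon harms, and that an observed zero needs an interval beside it.

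**The case against.** The strongest reply is that the harm of most interest is already asked about. A flare after loading a numbed tendon would most likely appear as increased pain, which the enquiry names as an example. Both contacts also come after the block should have worn off. This stands. A reader might infer that AT flares go unrecorded, but the text does not support that. What remains is that task-attributed or non-pain harm may be missed, and that pain recorded as injection-related may have come from the tasks.

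A second reply concerns the controls. A reader might infer that asking them would supply the missing reference for AT flares, or would separate injection effects from testing effects. It would do neither. Controls have no Achilles tendinopathy pain and no injection, and the groups are not randomized, so any difference would mix disease with injection. Separating the two would need AT participants tested without the block, which this design does not include. Controls also have no 1-day contact to set against the AT one.

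A third reply concerns two further inferences. One is that an unseen flare could sit beside the 1-week pain catastrophizing score; but AT participants are asked about increased pain at that same time. The other is a count of missed events, which would need a flare rate and a misattribution rate. The documents give neither.

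Finally, the document is a short summary. It gives the purpose of the contact, not the wording of the question, and does not say who judges relatedness. This also stands: the point is that no other enquiry is described, not that none took place.

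**Conclusion.** The point holds in a limited form, as a cheap improvement. As described, adverse events are sought only in AT participants and only as injection-related. No enquiry is described for harm attributed to the repeated tasks, some of them done under the block, or for any harm in controls.

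The number of events affected cannot be estimated from the documents. The 12.2% upper bound for zero events in 23 reflects the size of the group and not the wording of the question. The sample size, the type I error rate and the analyses of the primary outcomes are untouched.

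The conclusion assumes that the Study design section reports every adverse-event enquiry that was made. If a broader question was used in practice, saying so would settle the matter.

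**What to change.** At the contacts already planned (AT at 1 day and 1 week, controls at 1 week), ask every participant one open question about any adverse event or increase in pain since testing. Record the presumed cause afterwards as injection, testing or other. Tabulate events descriptively by group with exact confidence intervals, and state that control events give only a background rate of soreness after testing.

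The cost is one question within existing contacts and a short table. No extra visit is needed, and the sample size and alpha do not change. The small downside is that more minor events will be recorded.

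The document is written in the past tense, so the contacts may already be complete. In that case the remedy is in the reporting: state that harms were solicited only in AT participants and only as injection-related, and do not make an unqualified statement that there were no adverse events.

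### The stated 80% power and Table 1's detectable differences rest on an unadjusted 0.05, while the planned tests are Bonferroni-adjusted; the test that answers Aim 1.2 is not named

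*Combined protocol and SAP*

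**What the plan says.** All the relevant text is in the Statistical Analysis section of the combined protocol and SAP.

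- **Power.** Twenty per group is said to give at least 80% power, "and statistical significance defined as $P \leq 0.05", for effects no larger than published ones. Table 1 has two blocks: "Specific Aim 1.1, n=40, between groups, detectable effect size ≥ 0.91" and "Specific Aim 1.2, n=20, repeated measures, detectable effect size ≥ 0.68". Each covers pressure pain threshold (PPT), the kinesiophobia score (TSK) and ankle power, which the table labels primary.
- **Model.** "Mixed effects ANOVAs were used to examine the effects of group, time, and a group*time interaction".
- **ANOVA multiplicity.** The type I error rate is held at 0.05 "using Bonferroni adjustment for multiple comparisons (3 tests for motor performance, 2 tests for pain psychology, 3 tests for quantitative sensory testing").
- **Post-hoc multiplicity.** "Post-hoc comparisons were performed to examine significant interaction effects", with p-values adjusted "for the number of time points compared (2 for TSK, 3 for PCS, 4 for quantitative sensory test"). No divisor is listed for ankle power.
- **Recruitment.** After three participants with Achilles tendinopathy (AT) had too little relief from the injection, "an additional 3 participants were recruited per group to ensure adequate power, resulting in a final sample size of 46".

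**The concern.** The significance level used to size the study is not the level at which its outcomes are tested. The ANOVA divisors imply 0.05/3 = 0.0167 for PPT and ankle power and 0.05/2 = 0.025 for TSK. The post-hoc divisors imply 0.05/4 = 0.0125 for PPT and 0.025 for TSK. If the power figures were computed at 0.05, the design has less power than stated for the contrast it was sized on, and the claim that detectable effects do not exceed published ones may fail.

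A second gap makes Aim 1.2 hard to correct. Table 1 calls it a repeated-measures contrast in 20 people, but the text does not say whether the group-by-time interaction or a within-AT change answers it. The two have different alphas and different power.

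What is at stake is the reading of a null result: it could be presented as coming from a test with at least 80% power when that figure belongs to another alpha.

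**Working it through.** **Method.** Noncentral-t power, two-sided. The document does not state sidedness; two-sided is assumed because it reproduces 0.91 (one-sided 0.05 would give 88.1% power there).

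- Two groups: noncentrality = d × √(n₁n₂/(n₁+n₂)), df = n₁+n₂−2.
- Paired: noncentrality = d × √n, df = n−1.
- Detectable difference = d at 80% power × SD. Products below use unrounded d.

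**Inputs (Table 1).** Aim 1.1 SDs are 174.8 kPa, 5.7 and 0.9 W/kg; published differences are 171.8 kPa, 5.6 and 0.9 W/kg, so d = 0.983, 0.982 and 1.0. Aim 1.2 SDs are 28%, 5.7 and 0.9 W/kg; published differences are 25.8%, 5.6 and 0.9 W/kg, so d = 0.921, 0.982 and 1.0. Results below are in the order PPT, TSK, ankle power.

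**Step 1: reproduce the plan at unadjusted 0.05.**

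- Aim 1.1, 20/20: power at d = 0.91 is 80.1%; detectable d = 0.909. Then 0.909 × 174.8 = 158.9 kPa, 0.909 × 5.7 = 5.2 and 0.909 × 0.9 = 0.8, as printed.
- Aim 1.2, paired, n = 20: power at d = 0.68 is 82.2%; detectable d = 0.660. Then 0.660 × 5.7 = 3.8 and 0.660 × 0.9 = 0.6, as printed. For PPT, 0.660 × 28% = 18.5%; the printed 19% matches 0.68 × 28%.

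**Step 2: Aim 1.1 two-group contrast at 0.0167 / 0.025 / 0.0167.** At 20/20, power at d = 0.91 is 64.6% (0.0167) or 70.6% (0.025).

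| Per group | Detectable d (0.0167; 0.025) | Detectable difference | Power at published difference |
|---|---|---|---|
| 20/20 | 1.064; 1.009 | 185.9 kPa, 5.75, 0.96 W/kg | 72.4%, 77.7%, 74.2% |
| 20/23 | 1.025; 0.973 | 179.2 kPa, 5.54, 0.92 W/kg | 76.0%, 80.9%, 77.7% |
| 23/23 | 0.986; 0.936 | 172.4 kPa, 5.34, 0.89 W/kg | 79.7%, 84.0%, 81.2% |

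**Step 3: the planned ANOVA group effect.** This averages time points. Assuming two measurements with within-person correlation ρ and a difference that persists, effective d = d/√((1+ρ)/2). For PPT at ρ = 0.7: 0.983/√0.85 = 1.066. If the difference halves after injection, the average difference is (1 + 0.5)/2 = 0.75 of the published one. Power at the published differences:

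| Assumption | 20/20 | 23/23 |
|---|---|---|
| ρ = 0.7, persists | 80.2%, 84.5%, 81.7% | 86.5%, 89.8%, 87.8% |
| ρ = 0.9, persists | 75.0%, 79.9%, 76.6% | 81.9%, 86.0%, 83.4% |
| ρ = 0.7, halves | 51.6%, 58.0%, 53.2% | 59.1%, 65.2%, 60.8% |

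**Step 4: Aim 1.2 under each reading.**

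(a) *Within-AT post-hoc change.* With n = 20, PPT at 0.0125 detects 0.815 × 28% = 22.8% and TSK at 0.025 detects 0.739 × 5.7 = 4.2. Both are below the published values, where power is 89.9% and 96.8%. With n = 23 the figures are 21.0% and 3.9. Ankle power has no divisor: assuming 1 gives 0.59 W/kg, assuming 2 gives 0.67 W/kg (n = 20). At the stated d = 0.68 and n = 20, power is 72.4% (0.025) or 61.5% (0.0125).

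(b) *Interaction*, as a two-group contrast of change scores. This assumes Table 1's SDs are SDs of change and controls do not change.

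| Per group | Detectable difference | Power at published difference |
|---|---|---|
| 20/20 | 29.8%, 5.75, 0.96 W/kg | 65.9%, 77.7%, 74.2% |
| 20/23 | 28.7%, 5.54, 0.92 W/kg | 69.6%, 80.9%, 77.7% |
| 23/23 | 27.6%, 5.34, 0.89 W/kg | 73.5%, 84.0%, 81.2% |

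Table 1 uses the same SDs in both aims for TSK and ankle power. If those are between-person SDs, the SD of change is SD × √(2(1−ρ)). Setting 1.009 × √(2(1−ρ)) = 0.982 gives ρ = 0.53 for TSK; setting 1.064 × √(2(1−ρ)) = 1.0 gives ρ = 0.56 for ankle power. Above those values the interaction meets the plan's criterion at 20/20.

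**The case against.** The mismatch itself is hard to dispute; the case against concerns its size.

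- **The lowest figures are taken at the plan's smallest effect.** At the published differences the 20/20 shortfall is milder. This is right, and those are the fairer figures for the plan's own criterion, but all three stay below 80%.
- **No outcome is analysed by t-test.** The group effect in the mixed ANOVA could exceed 80% at 20 per group. It could also fall well short. The document gives neither the correlation nor the expected persistence, so it does not support 80% for that model.
- **Forty-six people were recruited, not 40.** At 23/23 the gap almost closes. However, the additions were made because of three AT participants with insufficient relief, and the text does not say whether those three stayed in the analysis. At 20/23, PPT misses by 7.4 kPa and ankle power by 0.02 W/kg.
- **"n=20" most naturally means a one-group contrast.** That is a reasonable reading, and PPT and TSK are then adequately powered at the published effects. But such comparisons are described as following a significant interaction, so the interaction still matters.
- **The interaction shortfall depends on the SD assumption.** This stands: with between-person SDs and ρ = 0.7, interaction power at 20/20 is 94.9% for TSK and 93.7% for ankle power.
- **The Aim 1.2 effect is printed as 0.68, not 0.660.** True (0.680 corresponds to n = 19), but n = 20 at d = 0.68 still clears 80% at 0.05 and not at 0.025 or 0.0125.

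**Conclusion.** The concern holds and should be fixed. For the two-group contrast on which Aim 1.1 was sized, the stated power of at least 80% is not available at the testing alpha with 20 per group, and the criterion that detectable effects do not exceed published ones fails for all three primary outcomes. At 23 per group the failure shrinks to PPT alone, by 172.4 − 171.8 = 0.6 kPa. For the ANOVA group effect actually planned, power is undetermined from the document.

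For Aim 1.2 the conclusion turns on the unnamed test: adequate for PPT and TSK as a within-AT post-hoc change, and short at 20 per group as an interaction if the tabulated SDs are SDs of change.

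These results assume two-sided tests, the Table 1 SDs, and Bonferroni applied as 0.05 over the listed divisors. The problem bears on how null findings are interpreted; positive findings passed the stricter level and are unaffected.

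**What to change.** Keep both Bonferroni rules and add no participants.

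1. State that 20 per group was computed at unadjusted two-sided 0.05, and that the ANOVAs were tested at 0.0167 (motor, sensory) and 0.025 (psychology).
2. Replace the Aim 1.1 power and detectable differences with the row of the Step 2 table that matches the numbers analysed, labelled as t-test contrasts. Add that mixed-ANOVA power depends on the within-person correlation.
3. Name the test for Aim 1.2 and restate its row at that test's own level. If it is the within-AT post-hoc change, use the figures in Step 4(a), give the ankle-power divisor, and say that the comparison follows a significant interaction. If it is the interaction, use Step 4(b) with the SD-of-change assumption stated. If the test is chosen after the results are known, say so.

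The cost is two sentences and a recomputed table. The stated figures become less favourable, and the sponsor must commit to one test for Aim 1.2.

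### Does recruiting 3 extra participants per group after 3 inadequate blocks mean that the AT group is analysed only where the injection worked?

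*Combined protocol and SAP*

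**What the plan says.** The Statistical Analysis section first gives the planned size: "A priori power analysis determined that a sample size of 20 per group was needed to detect effect sizes" of 0.91 between groups and 0.68 between repeat tests, at 80% power and a 0.05 significance level. It then explains the increase: "Because 3 participants with AT had insufficient pain relief from the" injection, "an additional 3 participants were recruited per group to ensure adequate power, resulting in a final sample size of 46".

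The tests follow directly. Pain: "Changes in Achilles tendon pain from pre-injection to post-injection were compared with Wilcoxon Signed Ranks tests". Motor, psychological and sensory outcomes: mixed effects ANOVAs with group, time and their interaction, where "The type I error rate for the ANOVAs was maintained at 0.05 by using Bonferroni adjustment for multiple comparisons". Correlations: "Pearson correlations examined relationships between the magnitude of change with an anesthetic injection of identified indicators of altered central processing in the AT group". None of these sentences names an analysis set, and no threshold for insufficient relief is given.

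In Study design, the injection is the only procedural difference between the groups, and the caption to Figure 1 says "All participants completed two sets of testing".

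**The concern.** Extra recruitment prompted by failed blocks, and justified by power, reads like replacement: 3 out, 3 in, AT back to 20. If so, AT participants are kept or dropped on a response measured after the injection. Controls have no injection and cannot fail that criterion, and adding 3 controls does not undo the selection.

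Three things would be at stake. The pain test would be run on a group chosen by its own outcome. Pre/post and group-by-time estimates would move in the direction that goes with relief, for any outcome correlated with relief. The correlations between change scores would come from a group with a narrower spread of relief. A Bonferroni adjustment corrects none of this.

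**Working it through.** **Inputs from the documents.** 20 per group planned; standardized effects 0.91 (between groups) and 0.68 (repeated measures); power at least 80%; level 0.05, taken as two-sided; 3 AT participants with insufficient relief; 3 added per group; final total 46.

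**Inputs assumed.** Normal changes; correlation r between pain change and outcome change of 0.3, 0.5 or 0.7; the 3 are the least relieved of 23. The documents give none of these.

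**1. The plan's own figures.** The noncentral t has noncentrality d/√(1/n₁+1/n₂) between groups and d√n for paired data.
- 20 v 20, d = 0.91: power 80.1%. Paired, n = 20, d = 0.68: power 82.2%. The planned size is reproduced.
- 2 × (20 + 3) = 46. The final size is reproduced.

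**2. Does the power argument show replacement?**

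| Set analysed | Between groups, d = 0.91 | Paired AT, d = 0.68 |
|---|---|---|
| No additions, 3 left out (17 v 20) | 76.5% | 74.9% |
| Additions, 3 left out (20 v 23) | 82.8% | 82.2% |
| All 46 (23 v 23) | 85.5% | 87.6% |

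The first row favours replacement, because power drops below 80% if the 3 go. The table, however, holds d fixed. If the 3 stay in and do not change, while the others change by 0.68 SD (an assumption), the AT mean is diluted:
- n = 20: 0.68 × 17/20 = 0.58 SD; simulated paired power about 67%.
- n = 23: 0.68 × 20/23 = 0.59 SD; simulated paired power about 76%.

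So keeping everyone also costs power and also gives a reason to recruit, although 3 more does not fully restore 80%. The control group points the same way: replacing 3 AT participants needs no new controls, since 20 v 20 already gives 80.1%. The text fits both readings.

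**3. Size if the 3 are left out.** The mean of the lowest 3 of 23 standard normal values is about −1.54, so dropping them raises the mean of the other 20 by 3 × 1.54/20 = 0.23 SD of pain change. An outcome shifts by r × 0.23:

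| r | Shift in AT outcome change | Group × time false positives at 0.025 | At 0.0167 |
|---|---|---|---|
| 0.3 | 0.07 SD | 2.9% | 2.0% |
| 0.5 | 0.12 SD | 3.7% | 2.6% |
| 0.7 | 0.16 SD | 5.1% | 3.6% |

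These rates come from simulated t tests on change scores, 20 v 23, with no true change in the outcome. That equals the interaction test when there are two time points. The levels are 0.05/2 (pain psychology, 2 tests) and 0.05/3 (motor performance, 3 tests). Outcomes with more time points were not simulated.

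Against the detectable 0.68 SD, the shifts are 0.07/0.68 = 10% to 0.16/0.68 = 24%. I leave them in SD units: for TSK and ankle power, Table 1 uses the same SDs (5.7 and 0.9 W/kg) in Aim 1.2 as in Aim 1.1, so these need not be SDs of change.

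The 0.23 is towards the upper end. If the 3 are a random draw from the lowest 6 or the lowest 10 of 23, the shift in pain change is 0.18 or 0.13 SD.

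**4. Correlations.** Expected r between two indicators, all 23 against the 20 kept:

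| Correlations with pain change | True r between indicators | n = 23 | n = 20 |
|---|---|---|---|
| 0.5 and 0.5 | 0.5 | 0.49 | 0.45 |
| 0.7 and 0.7 | 0.3 | 0.29 | 0.17 |
| 0.7 and 0 | 0.5 | 0.49 | 0.53 |

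The second row implies a partial correlation given pain change of (0.3 − 0.49)/(1 − 0.49) = −0.37, an unusual structure. The third row moves upward. The direction is not known in advance.

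**The case for a change.** The strongest case for a change is that a reader cannot tell which set lies behind any result, and that the remedy is almost free. Both sets of tests were completed by everyone, so the all-injected analysis needs no new data. Naming the set for each test, defining insufficient relief, and showing 23 v 23 beside any analysis of 20 would settle the matter. At r = 0.7 the per-test false-positive rate roughly doubles.

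Part of this stands. The analysis set is unstated and the criterion is undefined. If any reported analysis leaves out the 3, giving the number analysed and the all-injected result beside it is good reporting.

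The rest does not carry. Every bias figure depends on an exclusion that the text never makes. The doubling needs the top of an assumed range of correlations together with no mean change in the outcome. If relief drives the outcome and relief occurs on average, that null is false and a rejection is not a false positive. Nor is all 23 the only valid lead set: what happens when the pain is removed, and what happens after an injection whether or not it works, are both fair questions, and no randomization is broken by asking the first. The pain test's conclusion is also safe: at an assumed true mean change of 1.0 SD, the Wilcoxon test rejects in over 99% of simulated trials with either 20 or 23.

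**Conclusion.** No change to the plan follows. The sample-size figures reproduce. The final sample is stated as 46, with 3 added to both groups, and read literally that is 23 v 23 with no selection. If the 3 are set aside, the trial answers a narrower mechanistic question. The price is a shift of 0.07 to 0.16 SD in mean AT change and at most a rise from 2.5% to about 5.1% in the group-by-time false-positive rate for a two-time-point outcome tested at 0.025. These figures assume normal changes, correlations of 0.3 to 0.7 with pain change, and that the 3 are exactly the least relieved of 23. Choosing between the two sets is a trade-off over the question asked, not an error. The missing detail is of low severity, and analysts would settle it by giving the relief criterion and the number analysed with each result.

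### Holm's step-down procedure would keep the same family-wise 0.05 as the planned Bonferroni adjustment and is never less powerful: a cheap improvement worth 0 to about 9 points of power per outcome

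*Combined protocol and SAP*

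**What the plan says.** All the relevant text is in the Statistical Analysis section of the combined protocol and SAP.

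- **ANOVA families.** "The type I error rate for the ANOVAs was maintained at 0.05 by using Bonferroni adjustment for multiple comparisons". The families are given as "3 tests for motor performance, 2 tests for pain psychology, 3 tests for quantitative sensory testing", so the per-test levels are 0.05/3 = 0.0167, 0.05/2 = 0.025 and 0.0167.
- **Post-hoc comparisons.** These follow significant interactions, and their "p-values were adjusted using a Bonferroni adjustment for the number of time points compared": 2 for TSK, 3 for PCS and 4 for quantitative sensory testing.
- **Power.** "A priori power analysis determined that a sample size of 20 per group was needed", for effect sizes of "between groups ≥ 0.91 , between repeat tests ≥ 0.68", with power of at least 80% at P ≤ 0.05. Recruitment was later extended: "an additional 3 participants were recruited per group to ensure adequate power, resulting in a final sample size of 46", that is 23 per group.
- **Planning effects.** Table 1 gives one variable per domain: PPT (sensory), TSK (psychology) and ankle power (motor).

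No step-down procedure is mentioned anywhere.

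**The concern.** Single-step Bonferroni compares every p-value in a family of m tests with 0.05/m, whatever the other tests show. Holm starts at the same threshold for the smallest p-value and relaxes it after each rejection. For three tests the ordered p-values meet 0.05/3, 0.05/2 and 0.05, and testing stops at the first failure. Both methods bound the family-wise error at 0.05 under any dependence between outcomes. Any test that Bonferroni rejects, Holm rejects too.

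The plan's stated aim, a type I error rate of 0.05 within each domain, is therefore met equally well by a procedure that can only add rejections. With 20 to 23 participants per group, that may matter. What is at stake is efficiency: the chance of confirming a second or third real difference within a domain. The validity of the planned tests is not in question.

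**Working it through.** **Inputs.** From the Statistical Analysis section and Table 1: d = 0.91 between groups, 20 per group planned and 23 final, families of 3, 2 and 3 tests, alpha 0.05. Assumed, because the documents do not say: two-sided tests; a two-sample t-test in place of the ANOVA group effect; correlation between outcomes; and how many outcomes in a family have a real effect.

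**1. The plan's own figure.** With 20 per group the noncentrality is 0.91 × √(20/2) = 2.88 on 38 degrees of freedom. Power at two-sided 0.05 is 80.1%. The effect detectable at exactly 80% is 0.909, and 0.909 × 174.8 kPa = 158.9 kPa, as Table 1 shows. The paired case (n = 20, effect 0.68) gives 82.2%. The plan's figures reproduce.

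**2. Power at each threshold.** Write A, B and C for the power at 0.0167, 0.025 and 0.05.
- 20 per group: A = 0.646, B = 0.706, C = 0.801.
- 23 per group: A = 0.723, B = 0.775, C = 0.855.

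Under Bonferroni, per-outcome power is A in a 3-test family and B in the 2-test family.

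**3. Holm by hand, uncorrelated outcomes, 20 per group.** An outcome is rejected if its p-value is at most 0.0167; or lies between 0.0167 and 0.025 and at least one other is at most 0.0167; or lies between 0.025 and 0.05 and both others have already been rejected. Sums below use unrounded terms.
- All three real: A + (B − A)[1 − (1 − A)²] + (C − B)[B² − (B − A)²] = 0.646 + 0.052 + 0.047 = 0.745, a gain of 9.9 points.
- Two of three real: 0.646 + 0.060 × (1 − 0.354 × 0.983) + 0.095 × (0.706 × 0.025 − 0.060 × 0.0083) = 0.687, a gain of 4.0 points.
- One of three real: 0.646 + 0.060 × (1 − 0.983²) + 0.095 × (0.025² − 0.0083²) = 0.648, a gain of 0.2 points.
- Two tests, both real: B + (C − B)B = 0.706 + 0.095 × 0.706 = 0.773, a gain of 6.7 points.
- Two tests, one real: 0.706 + 0.095 × 0.025 = 0.708, a gain of 0.2 points.

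**4. Correlated outcomes.** Simulation at an assumed correlation of 0.3 (60,000 or more trials per case), mean power over the outcomes with a real effect, Bonferroni then Holm:

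| Family | Effects of 0.91 | 20 per group | 23 per group |
|---|---|---|---|
| 3 tests | all three | 64.5% → 73.5% | 72.2% → 80.8% |
| 3 tests | two of three | 64.7% → 68.5% | 72.5% → 76.1% |
| 3 tests | one of three | 64.8% → 65.0% | 72.2% → 72.4% |
| 2 tests | both | 70.7% → 76.8% | 77.7% → 83.3% |
| 2 tests | one of two | 70.5% → 70.7% | 77.7% → 77.9% |

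At 20 per group, over correlations 0 to 0.8, the gain with all three real runs from 9.9 down to 7.1 points, with both of two real from 6.8 to 4.8, and with two of three real from 4.0 to 3.1.

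**5. Intermediate case.** If one outcome in a 3-test family has 0.91 and the other two have 0.5, Holm gains that outcome about 2 points. If the other two have 0.3, it gains about 0.6.

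**6. What does not change.** Both methods test the smallest p-value at 0.05/m, so the chance of at least one rejection in a family is identical: 1 − (1 − 0.646)³ = 95.6% with three real, uncorrelated effects at 20 per group. Simulated family-wise error stays at or below 0.05 for both. Holm uses more of the allowance when some effects are real (4.4% against 3.3% with one of three real and uncorrelated outcomes), but the guarantee is the same.

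**7. Repeat-test effects.** Paired t-tests at 0.68 (n = 20) show the same pattern: 7.5 to 10.7 points with three of three real, 5.0 to 7.1 with two of two, and 0.2 or less with one real.

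**The case against.** The strongest reply is that Bonferroni does what the plan says it does, so this is a preference between two valid methods. That stands: nothing here is biased or contradictory.

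A reader might also infer that each primary outcome in Table 1 loses about 9 points of power. The documents do not support that. PPT, TSK and ankle power sit in three different families, and Table 1 gives no planning effect for the other outcomes in those families. Holm helps a primary outcome only if its family-mates are also significant. The 9 points need a 3-test family with all three effects near 0.91. That assumption matters far more than the correlation does.

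Three further limits stand.
- Bonferroni has simple matching simultaneous confidence intervals and Holm does not, so the power is not given up for nothing. The plan does not mention simultaneous intervals, which limits the weight of this here.
- The t-tests are a stand-in for mixed ANOVAs. No effect size is given for the group-by-time interaction, and no gain is computed for the post-hoc families. The ordering of the two methods holds there, but not these figures.
- The document is dated 4/29/19, is written in the past tense and reports a final sample of 46. A change to a less conservative method at that stage could look data-driven.

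None of this removes the main point: Holm never loses a rejection that Bonferroni makes, and its error guarantee is the same.

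**Conclusion.** The point holds as a cheap improvement, not as an error in the plan. At d = 0.91 and an assumed correlation of 0.3, Holm adds up to about 9 points of per-outcome power in a 3-test family with all three effects real, about 6 in the 2-test family with both real, about 4 with two of three real, and about 0 with one real. The documents do not show which of these cases applies.

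Two stronger inferences should be resisted. Holm would not in general bring power to the 80% target: at 23 per group a 3-test family reaches about 81% only if all three effects are real, and stays at 76% or 72% with two or one. The gap between planning at 0.05 and testing at 0.0167 or 0.025 (80.1% against 64.6% or 70.6% at 20 per group) is a separate matter, and Holm recovers only part of it. Nor should weight be placed on the chance that all three outcomes in a domain are significant, because the plan sets no such goal.

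**What to change.** In the Statistical Analysis section, replace Bonferroni with Holm step-down for the three ANOVA families and the post-hoc families, keeping the family sizes as they are. Report Holm-adjusted p-values, with unadjusted 95% confidence intervals labelled as such. For three tests, state that the ordered p-values are compared with 0.05/3, 0.05/2 and 0.05, stopping at the first failure.

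If any results had been seen before the change, keep the Bonferroni results as the planned analysis and report Holm beside them, labelled as a sensitivity analysis. State in the text which of the two situations applies.

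The cost is a wording change and one software option, with no added participants. The downside is the loss of simple simultaneous intervals that match the tests.
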